11 STATISTICAL CONSIDERATIONS

Data will be collected, checked, and entered into and a data management system in a Microsoft ACCESS database with identity and time stamping. All patients will be assigned a unique identifier (Personal Identification or PID) which will be the link for all databases and appear on all derived biospecimens. We will use filters for the invalid entries and the identification of missing and out-of-range values and a double data entry system. All inconsistencies between entries must be resolved with differences able to be reviewed by supervisors and auditors. Access to the database will be restricted combined physical access restriction and password protection. Analyses will be conducted in STATA and SAS.

11.1 Study Hypotheses and Analysis

A. The primary hypotheses are that *L. reuteri* therapy at the specified dose is safe and well-tolerated in children aged 2-24 months. There are three areas of safety and tolerability that will be assessed in this Phase 1 trial.

- 1. Evidence of bacteremia or invasive infection resulting from the administration of *L. reuteri* 17938.** Baseline and daily temperature measurements will be made during the study period during the product administration phase and then on all scheduled home visits. Complete blood counts with differential counts will be obtained at baseline, on day 5, and on day 28. The evaluation of all documented febrile episodes will include an examination by a physician, and thick smear for malaria, and blood culture for the evaluation of bacteremia if the temperature is greater than 39°C using temporal artery probe measures.

Specific outcome parameters in this category include:

- a. Mean daily temperature
- b. Incidence of fever on study days 1-5
- c. Frequency of temperature readings categorized as fever (adjusted for number of subjects per group)
- d. Number of episodes of *L. reuteri* bacteremia

2. Evidence of toxicity resulting from the *L. reuteri* DSM 17938 preparation.
Participants will have baseline, day 5, and day 28 assessment of hematologic status and

1 renal and hepatic function. Assessment of renal function will include blood urea nitrogen
2 (BUN) and creatinine (Cr). Assessment of hepatotoxicity will include transaminases
3 (AST, ALT) and total bilirubin. Hematologic status will be determined by CBC to
4 measure hemoglobin count and absolute neutrophil count, as mentioned above.

5
6 Specific outcome parameters in this category include:

7
8 a. Mean values for laboratory tests monitored (adjusted for number of subjects per
9 group). These are listed in Appendix D.
10 b. Frequency of out of range values for laboratory tests monitored (adjusted for number
11 of subjects per group). These are listed in Appendix D.

12
13 2. **Clinical tolerance.** The inclusion of a placebo group will allow for comparisons of the
14 prevalence of daily symptom measurements between treatment groups. The
15 symptoms monitored on the daily diary card (fever, anorexia/decreased oral intake,
16 vomiting, diarrhea, irritability, rash, itching, wheezing) are graded by the parent(s) of
17 the participant as mild, moderate, severe, or very severe. Parents report of severity
18 will be analyzed, except in the case that the physician or study team deems them to be
19 more severe than reported (the study team may upgrade, but NOT downgrade the
20 severity of the symptom).

21
22 Specific outcome parameters in this category include:

23
24 a. Frequency and severity of symptoms monitored as AEs (adjusted for number of
25 subjects per group)
26 b. Frequency of all AEs (adjusted for number of subjects per group)
27 c. Frequency of SAEs (adjusted for number of subjects per group)

28
29 All continuous variables will be summarized using descriptive statistics including number
30 (N), mean, standard deviation (SD), median, maximum, and minimum. All categorical
31 variables will be summarized using frequency counts and percentages.

32
33 Changes from baseline temperature and fever graded by defined toxicity categories will
34 be summarized using descriptive statistics by treatment group.

35
36 Concomitant medications, including those taken prior to study drug administration, will be
37 listed by subject. All concomitant medications taken after initiation of the study treatment
38 will be tabulated overall and by formulation. The number and percentage of subjects who
39 take at least 1 concomitant medication and the number and percent of subjects who take
40 each specific concomitant medication will be presented.

41
42 Treatment-emergent AEs will be defined as any event with a start date occurring on or
43 after treatment Day 1 or, if pre-existing, worsening after treatment Day 1. If a subject
44 reports the same AE more than once, then that subject will only be counted once for the

1 summary of that AE, using the most severe intensity.

2
3 Treatment-emergent AEs will be summarized as follows to the DSMB during closed
4 sessions:

5 • All treatment-emergent AEs;
6 • All treatment-emergent AEs by intensity;
7 • SAEs;
8 • All treatment-emergent SAEs by relationship to study drug; and
9 • AEs that led to premature discontinuation of study drug.

10 All SAEs and AEs leading to premature withdrawal from the study will be listed.

11
12 Hematology and blood chemistry parameters will be summarized at baseline and at the
13 end of the study. Laboratory values and changes from baseline in laboratory values will
14 be summarized descriptively for all subjects and by treatment group. A summary of shifts
15 from baseline to final evaluation will be given for each parameter for all subjects and by
16 treatment group. The normal range for each parameter will be used to create categories
17 of low, normal, or high. Any result higher than the upper limit normal (ULN) will be
18 categorized as high, any result lower than the lower limit of normal (LLN) will be
19 categorized as low, and any result within the LLN and ULN will be categorized as normal.
20 The number and percentage of subjects in each shift category from baseline to final
21 evaluation will be shown for each parameter. Only the hematology and blood chemistry
22 tests with a numeric normal range and at least one follow-up value will be analyzed for
23 shifts from baseline. The number and percentage of subjects with clinically significant
24 values will be presented.

25
26 **B. The secondary outcome measurements** are

27
28 1. To determine the duration of shedding of *L. reuteri* DSM 17938 following controlled
29 administration.

30
31 Since the longitudinal nature of the repeated PCR assays results in correlated outcomes,
32 generalized estimating equations (GEE) will be used to model the binary response
33 whether subjects exhibited a positive PCR result during the various period of study. The
34 duration of shedding of *L. reuteri* will be assessed using Kaplan Meier Product limit
35 estimates.

36
37
38
39
40 **11.2 Sample Size Considerations**

1
2
3 The sample size for this Phase 1 safety trial in healthy children aged 2-24 months is
4 determined by historical precedent for safety in human use.

5
6 Enrollment for the prior Phase 1 studies in adults (Safety of LR in Healthy volunteers
7 #NCT00774163) and children (Safety of LR in healthy children 2 to 5 years of age in Peru
8 #NCT02124122) have been able to recruit and retain >95 subject (Phase 1 child study in
9 progress). We have high and similar rates of retention in our other studies with more
10 complexity and participant burden, even among our birth cohorts.³⁷

11
12 Missing data will not be imputed. Data will be analyzed per treatment group assignment
13 after the administration of a single dose of product for all safety and tolerability analyses.
14 Data regarding the duration of carriage will be restricted to those individuals who complete
15 5 days of therapy.

16
17 The amount of subjects in this study will likely be underpowered to detect differences in
18 most secondary outcomes. This is in part due to the lack of information on key
19 parameters needed for sample size calculations. For example, in this age and context, to
20 calculate the duration of *L. reuteri* carriage following administration it is not known how
21 many subjects will become positive for *L. reuteri* by PCR following administration.
22 Similarly, it is not known how frequent intermittent passage of *L. reuteri* positive stool is in
23 individuals in this community, although about 10% of individuals in this age range test
24 positive. This data collected as part of this Phase 1 study will provide important
25 information of use in subsequent phase 2 trial [Efficacy of *Lactobacillus reuteri* in healthy children aged
26 2-24 months in the treatment of environmental enteropathy] .

27

1
2
3
4 11.3 Planned Interim Analyses (if applicable)
5

6 No formal interim analyses are planned; however, accumulated phase 1 trial data will be
7 reviewed by treatment group every 3 months by the NIDDK and DSMB.
8
9

10 **11.3.1 Safety Review**
11
12

13 Subject accrual, status adherence data on visits and intervention, adverse events and
14 rates of adverse events will be reported to the DSMB every three months. SAEs will be
15 reported within 24 hours of occurrence. Details of the interval reports are specified in
16 the DSMP.
17

18 The study would be halted if two or more subjects develop a similar SAE for which the
19 relationship to the study product cannot be excluded. This would include, but not be
20 limited to bacteremia with the product strain.
21

22 Individuals with a SAE during the period of probiotic administration will have the
23 intervention stopped regardless of the determined relationship to the study product, but
24 follow-up monitoring visits and testing would be completed to the greatest extent
25 possible, and the SAE would be managed until resolved.
26

27 INS requests SAE reporting, annual reports, and study termination report. Annual
28 reporting to IRB is planned for Tulane, Johns Hopkins University and AB PRISMA.
29
30

1
2
3

5

6 **12 SOURCE DOCUMENTS AND ACCESS TO SOURCE 7 DATA/DOCUMENTS**

8

9 All participants will have a chart composed of a copy of the signed consent document, all
10 CRFs, clinical laboratory values (CBC, AST, ALT, BUN, Creatinine, and total bilirubin
11 and screening day 0 *L. reuteri* PCR status, but not subsequent Lr PCR tests), diagnostic
12 testing results performed as part of adverse event evaluations, and copies of hospital
13 records in the case of a SAE. These charts will be available for review by study
14 personnel, the Medical Monitor, the INS, the regional directorate of Health of Loreto,
15 authorized representatives of NIDDK, OHRP, and other Department of Health and
16 Human Services agencies, as applicable; the Ethics committee of AB PRISMA, and the
17 Institutional Review Boards of Johns Hopkins University and Tulane University. Study
18 source documents are stored in locked cabinets within locked rooms of private research
19 space when not being reviewed. Databases are present in restricted areas of these
20 buildings and are password protected.

21 The study product control, including the review of temperature and shipping logs, viability
22 tests, and product tracking logs are available for review by auditors from the agencies
23 mentioned above.

24 Tests related to PCR carriage are generated in experimental files. These results are
25 then matched to SID and transferred to the database (in the case of ELISA results) or
26 transferred via a access file in which the technician manually reads the photo file and
27 inputs the result by SID which is then added to the database. All experimental files are
28 available for review.

29 All source documents, with the exception of microbiome data, will have primary storage
30 at the laboratory and field sites in Iquitos Peru. Microbiome data will be stored in in the
31 absence of identifiers in commercial laboratories in the United States and on servers
32 located at Johns Hopkins University. The Laboratory and offices at AB PRISMA are
33 used for long term storage of physical documents and the secure storage of electronic
34 versions of the data on a server. The building has 24hr staff presence and is a private
35 facility with limited access.

6

7 13 QUALITY CONTROL AND QUALITY ASSURANCE

8

9 Quality Assurance

10 To ensure the quality and integrity of laboratory and clinical data, detailed SOPs will be
11 written to clarify correct procedures and handing of data and specimens that extends from
12 field activities to data management. Staff will be trained in CITI and the SOP portions that
13 correspond to their responsibilities in the study. Study responsibilities will be specified in
14 the Site personnel and signature log. Training will be documented and documentation will
15 consist of a training duration, specific areas covered in training, and register of
participants. This training, which will occur prior to the study and reinforced during the
study, will be documented in the study file for review by study monitors.

16

17 Laboratory protocols

18 Laboratory protocols for the collection, registration and barcoding of all biologic samples
19 will be detailed.

20

21 Product Assurance

22 The Certification of Assurance of the study product, obtained by the product supplier, will
23 contain the following information.

24

25 Identity

26 Identity of the test product will be confirmed by standard carbohydrate utilization tests (API
27 50CH test (BioMerieux) pattern and the plasmid profile of the strain will be documented.

28

29 Purity

30 Information on the content of *Salmonella*, *E. coli*, yeast and mold, and total aerobic count
31 per USP <61>.⁴³ Evaluation for contamination with *Shigella* will be by FDA protocol BAM
32 Chapter 6.). The release limit of *Salmonella*, *Shigella* and *E. coli* is absent in 10g of
33 product, yeast and mold < 100 CFU/g and total aerobic count < 1000 CFU/g.

34

35 Viable counts of probiotic product strain

36 Existing laboratory protocols will be employed, with modifications as necessary, for
37 quantification of the viable count of product strain (name protocol). Viable counts will be
38 performed prior to study enrollment and every month following study initiation until the last
39 dose of product is administered. Tolerance for variability will be \pm 1 log CFU count. If the
40 results are not within this range, the product will be re-analyzed from two vials from the
41 same stock. If again not within range, this stock will be discarded and replaced with new
42 study product provided by BioGaia, the product manufacturer.

43

44 All study personnel engaged in study activities must have training documented in the form

1 of signatures on training logs. For laboratory scientists, this includes practicums
2 demonstrating test proficiency in assay performance and the correct storage and naming
3 of experimental files. Upon completion of testing, they sign the SOP to acknowledge
4 proficiency certification and compliance with the protocol SOP.

5

6

7 **Quality Control**

8 CRFs and source documents will be reviewed for completeness by a field or data entry
9 personnel daily and forms will be reviewed on site by the Study Coordinator, the study
10 physician, and /or overseeing investigators. Upon completion, forms are further evaluated

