APPENDIX A.1: Planned laboratory tests	64
Appendix B. Definitions for Adverse Events Monitoring	65
APPENDIX C: Clinical adverse events to be monitored : Symptoms	66
APPENDIX D: LABORATORY VALUES	67
APPENDIX E. FEVER SEVERITY GRADING	69

LIST OF ABBREVIATIONS

[figure not shown]
AE	Adverse Event
CFR	Code of Federal Regulations
CIOMS	Council for International Organizations of Medical Sciences
CONSORT	Consolidated Standards of Reporting Trials
CRF	Case Report Form
DSMB	Data and Safety Monitoring Board
DSMP	Data Safety Monitoring Plan
EC	Ethics Committee
FWA	Federal-Wide Assurance
GCP	Good Clinical Practice
IATA	International Air Transit Association
ICH	International Conference on Harmonisation
IND	Investigational New Drug Application
INS	Peruvian National Institute of Health (Instituto Nacional de Salud)
IRB	Institutional Review Board
CITI	Collaborative Institutional Training Initiative
LR or Lr	Lactobacillus reuteri
MOP	Manual of Procedures
NIDDK	National Institute of Diabetes and Digestive and Kidney Diseases
NIH	National Institutes of Health
OHRP	Office for Human Research Protections
OHSR	Office of Human Subjects Research
PI	Principal Investigator
PID	Personal Identifying Code
PL	Placebo
QA	Quality Assurance
QC	Quality Control
SAE	Serious Adverse Event
SID	Specimen identification code
SOP	Standard Operating Procedure
WHO	World Health Organization

PROTOCOL SUMMARY

Title:	Safety of Lactobacillus reuteri in healthy children aged 2-24 months
Précis:	Phase I double blinded randomized trial of the safety and tolerability of Lactobacillus reuteri DSM 17938 given for five successive days in healthy children. Sixty children will receive study product at a treatment to placebo ratio of 2:1 and followed for 3 months for safety outcomes.

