3.2.1 Primary Outcome Measures

23
24 There are three major areas of safety and tolerability that will be assessed in this phase I
25 trial. The outcome measurements will be compared between the two treatment groups
(Intervention v placebo) with intent to treat analysis.

26
27
28 **1. Evidence of invasive infection resulting from the administration of *L. reuteri* DSM
29 17938.** Baseline and daily temperature measurements will be made during the study
30 period. Complete hemogram with differential count obtained at baseline, on day 5, and
31 on day 28. Vital signs will be monitored daily during the administration of the treatment
32 (days 1-5). The evaluation of all febrile episodes will be done and include a physician
33 exam and the evaluation of blood smears for malaria and blood cultures for the
34 evaluation of possible bacteremia.

35
36 Specific outcome parameters in this category include:

37
38 a. Mean daily temperature
39 b. Incidence of fever on study days 1-5
40 c. Frequency of temperature readings categorized as fever (adjusted for number of
41 subjects per group)
42 d. Number of episodes of *L. reuteri* bacteremia

43
44 **2. Clinical tolerance.** The inclusion of a placebo group will allow for comparisons of daily
45 symptom measurements to be compared between the treatment and placebo group.
The symptoms will be monitored for at household visits, and will be graded as
adverse events according to defined criteria. Symptoms monitored as AEs include
fever, nausea/upset stomach, vomiting, diarrhea, irritability, rash, pruritis, and
wheezing or bronchospasm. Diagnostic microbiology will be performed on all stool
specimens from subjects who develop diarrhea during the 90 days following initiation
of therapy.

46
47 Specific outcome parameters in this category include:

- 1 a. Frequency and severity of symptoms monitored as AEs (adjusted for number of
2 subjects per group)
- 3 b. Frequency of all AEs (adjusted for number of subjects per group)
- 4 c. Frequency of SAEs (adjusted for number of subjects per group)

5

6

7 **3. Evidence of toxicity resulting from the *L. reuteri* DSM 17938 preparation.**

8 Participants will have baseline, day 5, and day 28 assessment of hematologic status and
9 renal and hepatic function. Assessment of renal function will include blood urea nitrogen
10 (BUN) and creatinine (Cr). Assessment of hepatic toxicity will include transaminases

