4 STUDY DESIGN

The study is a single center Phase 1 double blind placebo controlled trial of *Lactobacillus reuteri* DSM 17938 in children aged 2-24 months. The study population is based in a community with a registered clinical trial center in rural Peru where this protocol can be done in a highly controlled setting. The study is intended to enroll healthy children living in a resource constrained setting where chronic undernutrition and diarrheal disease is common, as this is the population that is most likely to receive benefit from the use of this and or other probiotic products for the treatment of acute infectious diarrhea and environmental enteropathy.

Up to 100 subjects will be enrolled in order to obtain the randomization of 60 subjects, who will receive study product or placebo at a ratio of 2:1. Participants will be enrolled between the ages of 8 weeks and 24 months. There will be no age stratification. Participants will be screened with a baseline history and physical examination and laboratory tests to determine the HIV status of the child, as well baseline laboratory tests to evaluate occult infections, hepatic function, and renal function. Upon randomization subjects will be screened and randomized to a treatment arm. Product will be administered under the direct supervision of study staff daily for 5 days. The primary outcome is the safety and tolerability of the product at this dose and formulation. Safety will be assessed by the monitoring of baseline laboratory tests at 5 and 28 days following the initiation of therapy and by AE monitoring. Tolerability will be evaluated by analyzing 28 day diary cards that are distributed to all randomized subjects on which parents record their child's symptoms (specifically fever, anorexia/oral intake, vomiting, diarrhea, irritability, rash, wheezing, or open fields which allows them to describe any issue their child may experience and grade its severity). Secondary outcomes include: 1) The assessment of the duration of shedding of *Lactobacillus reuteri* (Lr) strain DSM 17938 following administration. This will be determined by and endpoint PCR assay for *L. reuteri* done on stool collected on D3, D5, D12, D15, D18, D24, D28, D36 on all participants.

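### The plan promises a between-arm comparison of laboratory values and temperature but specifies no arm difference or interval; baseline is used only descriptively and age not at all.

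*Combined protocol and SAP*

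**What the plan says.** Section 3.2.1 states the intention: "The outcome measurements will be compared between the two treatment groups", by intent to treat. Section 11.1 opens with primary hypotheses of safety and tolerability. Its continuous parameters include "Mean daily temperature" and "Mean values for laboratory tests monitored (adjusted for number of subjects per" group.

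The methods in section 11.1 for these parameters are:

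- descriptive statistics (N, mean, SD, median, maximum, minimum) for every continuous variable;
- change from baseline temperature, summarised by treatment group;
- laboratory results: "Laboratory values and changes from baseline in laboratory values will" be summarised descriptively, overall and by group;
- tables of low/normal/high shifts from baseline to final evaluation, overall and by group.

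The laboratory paragraph speaks of baseline and the end of the study. It does not name Day 5, although blood is drawn then.

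On age, section 4 says "There will be no age stratification". Appendix D grades hemoglobin in two age bands, 2-5 and 6-24 months. Age appears in no planned comparison. Section 7.5 says iron supplementation will be controlled for in the clinical and laboratory outcomes at days 5 and 28. It gives no method, and section 11.1 does not take this up.

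**The concern.** The placebo arm is there to provide a contrast, and for laboratory toxicity that contrast is the main quantitative evidence. Section 11.1 names methods for the secondary shedding outcome (GEE and Kaplan-Meier), but no comparative method for any primary parameter. Two means with their SDs, side by side, do not say what difference between arms the data exclude. The stated adjustment for group size adds nothing to a mean, which already divides by n.

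The contrast matters more here because of selection at entry. Exclusion 9 admits only children whose leucocyte count, BUN, creatinine, AST, ALT and bilirubin are in range. Some of them will be out of range on retest, in both arms, through ordinary variation. A within-arm shift from normal to high therefore cannot be read as toxicity without the placebo figure beside it and an interval on the difference.

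A baseline value and an age will be on file for every child. Using them as covariates would sharpen the contrast and guard against a chance difference in age between small arms.

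**Working it through.** **No figure to reproduce.** Section 11.2 says the sample size is "determined by historical precedent for safety in human use" and gives no alpha, power, effect or SD. Section 4 sets 60 randomised, and the Protocol Summary a 2:1 ratio, so the arms are 40 and 20.

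**Precision.** Let r be the correlation between baseline and follow-up, with equal SDs at both times. In units of the outcome SD, the standard error of the arm difference is:

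- raw follow-up means: √(1/40 + 1/20) = √0.075 = 0.274
- change from baseline: 0.274 × √(2(1 − r))
- adjusted for baseline: 0.274 × √(1 − r²)

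The documents give no r, so a range is shown. Half-widths are 1.96 × SE.

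| r | SE raw | SE change | SE adjusted | 95% half-width raw / change / adjusted |
|---|---|---|---|---|
| 0.3 | 0.274 | 0.324 | 0.261 | 0.54 / 0.64 / 0.51 |
| 0.5 | 0.274 | 0.274 | 0.237 | 0.54 / 0.54 / 0.46 |
| 0.7 | 0.274 | 0.212 | 0.196 | 0.54 / 0.42 / 0.38 |

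A simulation of 20,000 trials at 40 and 20 gave adjusted SEs of 0.264, 0.239 and 0.197, so the small-sample penalty is about 1%.

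**Relative width.**

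- Adjusted against change is √((1 + r)/2): √0.65 = 0.806, √0.75 = 0.866, √0.85 = 0.922. The interval is 19%, 13% and 8% narrower.
- Adjusted against raw is √(1 − r²): 0.954, 0.866, 0.714. The interval is 5%, 13% and 29% narrower.

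The change score is itself less precise than the raw mean when r is below 0.5.

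**Effect of exclusion 9.** Suppose, as an assumption, that the top 5% of each test is cut off at baseline. A normal baseline variance then falls to 0.81 of its former value. With slope r and residual variance 1 − r² unchanged, the follow-up variance is 0.81r² + (1 − r²) and the change-score variance is 0.81(1 − r)² + (1 − r²). For r = 0.3, 0.5 and 0.7 in the unselected population:

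- the correlation among entrants falls to 0.27, 0.46 and 0.66;
- the gain against change scores becomes about 17%, 11% and 6%;
- the gain against raw means becomes about 4%, 11% and 25%.

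Hemoglobin is less affected, because exclusion 8 and section 7.3 remove only severe anemia.

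**Age.** If ages are uniform from 8 weeks to 24 months (an assumption), their SD is 6.4 months. The SE of the difference in mean age is 6.4 × 0.274 = 1.75 months, with a 95% range of ±3.4 months. At that limit, an outcome correlated 0.2, 0.4 or 0.6 with age has its raw arm difference moved by 0.2, 0.4 or 0.6 × 1.96 × 0.274 = 0.11, 0.21 or 0.32 SD.

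**The case against.** The strongest reply is that this is a 60-child Phase 1 trial, sized by precedent, with no powered hypothesis. Descriptive summaries are normal in such a trial, the placebo arm is reported alongside, and preferring covariate adjustment to change scores is a matter of efficiency. That limits the severity. It does not answer the missing interval, because the protocol itself promises a comparison.

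Several stronger readings are tempting, and the documents do not support them:

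- *Baseline is ignored.* It is not. Section 11.1 plans changes from baseline by group for both temperature and laboratory values, and laboratory shift tables. What is missing is its use as a covariate.
- *No covariate control is planned.* Section 7.5 promises control for iron supplementation, though without a method.
- *The gain is the full difference from raw means.* Change scores are also planned, so the smaller figures are the relevant ones wherever r exceeds 0.5.
- *The comparison is biased by age.* Randomisation keeps the arm difference unbiased on average; an age imbalance would be a chance event. Change scores would also remove much of any stable age difference in level over 28 days. The 1.5 g/dL gap in Appendix D (11 − 9.5) separates lower limits of normal, not mean hemoglobins.
- *A known share of children will drift out of range.* The direction is sure, the amount is not. It depends on tail size and correlations that the documents do not give.

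**Conclusion.** The point holds as a gap in specification and a loss of precision. No between-arm estimate or interval is defined for the laboratory and temperature means, baseline serves only descriptive summaries, and age is unused. With raw means the 95% half-width is about 0.54 SD. Baseline adjustment brings it to between 0.51 and 0.38 SD for r from 0.3 to 0.7. It is at least as precise as both the raw mean and the change score, apart from a small-sample cost of about 1% of the SE when r is near zero.

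These sizes rest on an assumed r, equal SDs at baseline and follow-up, and no dropout. The age figures also assume uniform ages. Selection by exclusion 9 probably puts the gain for tests other than hemoglobin below the headline figures. Severity is modest: the change is worth making because it is nearly free and supplies the interval that the promised comparison needs.

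**What to change.** Add to section 11.1:

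1. For each Appendix D test, at Day 5 and at Day 28 separately, fit a linear model of the follow-up value on arm, baseline value and age in months. Use the log scale for AST, ALT and bilirubin. Report the adjusted difference, or ratio for the logged tests, with its 95% interval.
2. Do the same for mean temperature over days 1-5, with baseline temperature as the covariate in place of the baseline laboratory value.
3. Report out-of-range frequencies as an arm risk difference with a score or exact 95% interval. Keep the shift tables as description.
4. Delete the adjustment for number of subjects where it is attached to means.
5. Reconcile the model with the iron control in section 7.5. That section starts study-supplied iron at least 5 days after the last dose, so it cannot affect Day 5 values. Because it can be triggered by the Day 5 hemoglobin, a post-randomisation result, a Day 28 sensitivity analysis is one suitable place for it.

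The cost is SAP wording, a few lines of code and two degrees of freedom per model. No new data are needed, and fixing the model now prevents a choice after unmasking.

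### No interval, test or model is named for any primary safety outcome, and the low-power caveat leaves the primary comparisons out, although 0 events in 40 active children would still be compatible with a true rate of up to 8.8%

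*Combined protocol and SAP*

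**What the plan says.** Section 11.1 (part A) states the primary hypothesis: *L. reuteri* "therapy at the specified dose is safe and well-tolerated in children aged 2-24 months". It attaches no numeric criterion. Section 3.2.1 adds that "The outcome measurements will be compared between the two treatment groups" by intent to treat.

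The methods offered for the primary outcomes, all in section 11.1, are:

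- Categorical outcomes: "variables will be summarized using frequency counts and percentages".
- Continuous outcomes: "All continuous variables will be summarized using descriptive statistics including number", mean, SD, median, maximum and minimum.
- Temperature and laboratory values: descriptive changes from baseline, with low/normal/high shift tables for the laboratory tests.

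Section 7.5 says that iron supplementation will be controlled for when adverse events are analysed, but names no model. GEE and Kaplan-Meier appear in section 11.1 only for the secondary shedding outcome.

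Section 11.2 says that the sample size is "determined by historical precedent for safety in human use". Its one remark on power begins "The amount of subjects in this study will likely be underpowered to detect differences in" and goes on to refer to most secondary outcomes. Section 3.2.2 lists a single secondary outcome.

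**The concern.** The plan states a hypothesis of safety and announces a between-arm comparison, but gives no way to express the uncertainty of either. A percentage from 40 children, or a pair of percentages from 40 and 20, does not show what the data rule out.

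This matters most for the harm that section 2.3.1 treats as the main risk, disseminated infection with the probiotic strain. The protocol describes it as rare, so no cases in 40 is a likely result whether or not there is a small real risk. Section 11.2 says that the data will inform a later phase 2 trial in children of the same age, and whoever plans that trial needs to know which rates have been excluded.

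The placing of the power caveat adds to the difficulty. By limiting it to secondary outcomes, section 11.2 says nothing about the primary comparisons, which rest on the same 60 children.

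**Working it through.** **Inputs from the documents.** Section 4 plans "randomization of 60 subjects, who will receive study product or placebo at a ratio of 2:1", and the Protocol Summary gives the same ratio. Active arm: 60 × 2/3 = 40. Placebo arm: 60 × 1/3 = 20. The documents give no alpha, power, event rate, margin or precision target for the primary outcomes, so there is no sample-size calculation to reproduce.

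**1. What zero events in one arm excludes.** The exact (Clopper-Pearson) upper limit for 0/n is 1 − a^(1/n), with a = 0.025 for a two-sided 95% interval and a = 0.05 for a one-sided 95% limit.

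- 0/40, two-sided: 1 − 0.025^(1/40) = 0.0881, or 8.8%.
- 0/40, one-sided: 1 − 0.05^(1/40) = 0.0722, or 7.2%.
- 0/20, two-sided: 1 − 0.025^(1/20) = 0.168, or 16.8%.

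The documents give no dropout rate. If 38 active children were evaluable, the limits for zero events would be 9.3% (two-sided) and 7.6% (one-sided). With 36 they would be 9.7% and 8.0%.

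Seen the other way round, a true rate of 5% produces no events in 40 children with probability 0.95^40 = 0.129, or 12.9%.

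**2. What a comparison of the arms excludes.** The Newcombe interval combines the Wilson limits of the two arms. For 0/n the Wilson lower limit is 0 and the upper limit is z²/(n + z²), with z² = 3.84.

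- Active 0/40: 3.84/43.84 = 0.088.
- Placebo 0/20: 3.84/23.84 = 0.161.
- Both observed rates and lower limits are zero, so the interval for active minus placebo is −0.161 to +0.088, or about −16 to +9 points.

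For commoner events the interval is wider. These observed rates are illustrations and do not come from the documents:

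| Active | Placebo | Observed difference | Newcombe 95% interval (points) |
|---|---|---|---|
| 0/40 | 0/20 | 0 | −16 to +9 |
| 8/40 (20%) | 4/20 (20%) | 0 | −24 to +19 |
| 12/40 (30%) | 6/20 (30%) | 0 | −25 to +22 |

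**3. Continuous outcomes.** For a difference in means with a common SD, the 95% half-width is t × SD × √(1/40 + 1/20). With t = 2.00 on 58 degrees of freedom this is 2.00 × 0.274 × SD, or about 0.55 SD.

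**4. Power, as an illustration only.** Assume a two-sided Fisher exact test at 5%, which the documents do not plan, and a range of placebo rates, which they do not give. Enumerating all outcomes for 40 v 20, the power to detect a true 20-point excess on active is:

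| Assumed placebo rate | Active rate | Power |
|---|---|---|
| 0% | 20% | 56% |
| 5% | 25% | 46% |
| 10% | 30% | 37% |
| 20% | 40% | 28% |
| 30% | 50% | 25% |

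With 0/20 on placebo, the smallest active count that reaches p ≤ 0.05 is 8/40 (p = 0.043); 7/40 gives p = 0.084.

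**The case against.** Descriptive safety summaries are usual in Phase 1. The sample size is openly based on precedent and no power is claimed for it. The DSMB reviews data by treatment group every three months, the study halts at two similar SAEs whose relation to the product cannot be excluded, and all SAEs are listed individually. The denominators will be reported, so a reader can work out the limits. Intervals for every symptom and test would mean dozens of them in 60 children.

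Much of this stands. Neither a larger trial nor a formal test is called for, and 60 is not an error. The intervals should be labelled descriptive. The monitoring rules protect children during the trial, but they do not say what the final data exclude. Leaving readers to derive the limits is a weak substitute when the plan itself states a hypothesis and a comparison.

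Three stronger readings are tempting, and the documents do not support them:

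- **That the primary results are counts and percentages and nothing else.** Continuous outcomes get means, SDs, changes from baseline and shift tables, and section 7.5 promises an adjustment for iron.
- **That zero events, or similar percentages in the two arms, would be declared safe.** No success criterion or equivalence rule is written. Nothing in the plan guards against that conclusion, but it would be the later author's step.
- **That the trial has a known, inadequate power.** No test is planned and no placebo rate is given, so the power figures only illustrate.

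**Conclusion.** The gap is real and inexpensive to close. The plan names no measure of precision and no method of comparison for any primary outcome, and its power caveat omits the primary comparisons.

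The size is firm where it depends only on the planned 40 and 20, assuming all are evaluable: up to 8.8% (two-sided) or 7.2% (one-sided) not excluded by 0/40, and about −16 to +9 points for 0/40 v 0/20. The power for a 20-point excess, 56% falling to 25% as the placebo rate goes from 0% to 30%, depends on the assumed test and rates and is secondary to the argument.

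**What to change.** In section 11.1, state that the following will be reported as descriptive estimates, with no multiplicity claim:

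- for each binary primary outcome (each SAE type, *L. reuteri* bacteremia, each solicited symptom, each out-of-range test), the active-arm rate with an exact 95% interval, and the active-minus-placebo difference with a Newcombe 95% interval;
- for temperature and each laboratory value, the difference in means with a 95% interval.

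In section 11.2, extend the low-power caveat to the primary between-arm comparisons, and state that 0/40 excludes only true rates above 8.8% (two-sided 95%).

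The cost is a few table columns and some sentences, and a stated conclusion that is less favourable than a bare zero. No extra children, visits or samples are needed.
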